#### 11.1.4.1 Evaluation of Target lesions by MRI using McDonalds criteria

Response	WHO/modified McDonald Criteria
CR (complete response)	Complete disappearance of all enhancing disease and off all steroids
PR (partial response)	<math>\geq 50\%</math> reduction in the sum of products of the perpendicular diameters of up to 2 target lesions* plus no new lesion, no progression of non-measurable CNS lesion, no increasing steroid requirements, and no worsening of neurologic symptoms
SD (stable disease)	$< 50\%$ reduction in size or $< 25\%$ increase in size.
PD † (progressive disease)	
 
• <math>\geq 25\%</math> increase of up to 2 target CNS lesions relative to nadir
 
• New CNS lesions
 
• unequivocal progression (defined below‡)
 
• Tumor-related increase in steroid dose
 
• New or worsening tumor-related neurologic symptoms
 

#### 11.1.4 Duration of Response

Duration of overall response: The duration of overall response is measured from the time measurement criteria are met for CR or PR (whichever is first recorded) until the first date that recurrent or progressive disease is objectively documented (taking as reference for progressive disease the smallest measurements recorded since the treatment started).

The duration of overall CR is measured from the time measurement criteria are first met for CR until the first date that progressive disease is objectively documented.

Duration of stable disease: Stable disease is measured from the start of the treatment until the criteria for progression are met, taking as reference the smallest measurements recorded since the treatment started, including the baseline measurements.

## **Evaluation of Best Overall Response**

The best overall response is the best response recorded from the start of the treatment until disease progression/recurrence (taking as reference for progressive disease the smallest measurements recorded since the treatment started). The patient's best response assignment will depend on the achievement of both measurement and confirmation criteria.

### **For Patients with Measurable Disease (i.e., Target Disease)**

Target lesions	Non-Target Lesions	New Lesions	Overall Response	Best Overall Response when Confirmation is Required*	
CR	CR	No	CR	$\geq$ 4 wks. Confirmation **	
CR	Non-CR/Non-PD	No	PR	$\geq$ 4 wks. Confirmation **	
CR	Not evaluated	No	PR		
PR	Non-CR/Non-PD/not evaluated	No	PR		
SD	Non-CR/Non-PD/not evaluated	No	SD	Documented at least once $\geq$ 4 wks from baseline **	
PD	Any	Yes or No	PD	No prior SD, PR or CR	
Any	PD ***	Yes or No	PD		
Any	Any	Yes	PD		

* See RECIST 1.1 manuscript for further details on what is evidence of a new lesion.
 
** Only for non-randomized trials with response as primary endpoint.
 
*** In exceptional circumstances, unequivocal progression in non-target lesions may be accepted as disease progression.
					

Note: Patients with a global deterioration of health status requiring discontinuation of treatment without objective evidence of disease progression at that time should be reported as "symptomatic deterioration." Every effort should be made to document the objective progression even after discontinuation of treatment.
					

## **11.2 Antitumor Effect – Non-CNS Metastases**

Although non CNS response is not the primary endpoint of this trial, subjects with measurable disease will be assessed by standard criteria. For the purposes of this study, subjects should be re-evaluated every 4 cycles of treatment.

Response and progression will be evaluated in this study using the new international criteria proposed by the revised Response Evaluation Criteria in Solid Tumors (RECIST) guideline (version 1.1) [Eur J Ca 45:228-247, 2009]. Changes in the largest diameter (unidimensional measurement) of the tumor lesions and the shortest diameter in the case of malignant lymph nodes are used in the RECIST criteria.

### **11.2.1 Definitions**

Evaluable for toxicity: All subjects will be evaluable for toxicity from the time of their first treatment with eribulin.

Evaluable for objective response: Only those subjects who have measurable disease present at baseline, have received at least one cycle of therapy, and have had their disease re-evaluated will be considered evaluable for response. These subjects will have their response classified according to the definitions stated below.

**Note:** Subjects who exhibit objective disease progression prior to the end of cycle 1 will also be considered evaluable.

Evaluable Non-Target Disease Response: Subjects who have lesions present at baseline that are evaluable, but do not meet the definitions of measurable disease, have received at least one cycle of therapy, and have had their disease re-evaluated will be considered evaluable for non-target disease. The response assessment is based on the presence, absence, or unequivocal progression of the lesions.

### **11.2.2 Disease Parameters**

Measurable Disease: Measurable lesions are defined as those that can be accurately measured in at least one dimension (longest diameter for non-nodal lesions and short axis for nodal lesions to be recorded) as  $> 20$  mm by chest x-ray, as  $> 10$  mm with CT scan, or  $> 10$  mm with calipers by clinical exam. All tumor measurements must be recorded in millimeters (or decimal fractions of centimeters).

Malignant lymph nodes: To be considered pathologically enlarged and measurable, a lymph node must be  $> 15$  mm in short axis when assessed by CT scan (CT scan slice thickness recommended to be no greater than 5 mm). At baseline and in follow-up, only the short axis will be measured and followed.

Non-measurable disease: All other lesions (or sites of disease), including small lesions (longest diameter  $< 10$  mm or pathological lymph nodes with  $> 10$  to  $< 15$  mm short axis) are considered non-measurable disease. Bone lesions, leptomeningeal disease, ascites, pleural/pericardial effusions, lymphangitis cutis/pulmonitis, inflammatory breast disease, and abdominal masses (not followed by CT or MRI) are considered as non-measurable.

Target lesions: All measurable lesions up to a maximum of 2 lesions per organ and 5 lesions in total, representative of all involved organs, should be identified as **target lesions** and recorded and measured at baseline. Target lesions should be selected on the basis of their size (lesions with the longest diameter), be representative of all involved organs, but in addition should be those that lend themselves to reproducible repeated measurements.

Non-target lesions: All other lesions (or sites of disease) including any measurable lesions over and above the 5 target lesions should be identified as **non-target lesions** and should also be recorded at baseline. Measurements of these lesions are not required, but the presence, absence, or in rare cases unequivocal progression of each should be noted throughout follow-up.

### **11.2.3 Response Criteria**

#### **Response Evaluation of Target Lesions**

Complete Response (CR):

Disappearance of all target lesions. Any pathological lymph nodes (whether target or non-target) must have reduction in short axis to  $< 10$  mm.

**Partial Response (PR):**

At least a 30% decrease in the sum of diameters of target lesions, taking as reference the baseline sum of diameters.

**Progressive Disease (PD):**

At least a 20% increase in the sum of diameters of target lesions, taking as reference the *smallest sum on study* (this includes the baseline sum if that is the smallest on study). In addition to the relative increase of 20%, the sum must also demonstrate an absolute increase of at least 5 mm.

**Note:** the appearance of one or more new lesions is also considered progression.

**Stable Disease (SD)"**

Neither sufficient shrinkage to qualify for PR nor sufficient increase to qualify for PD, taking as reference the smallest sum diameters while on study.

**Evaluation of Non-Target lesions**

**Response Evaluation of Non-Target Lesions**

**Complete Response (CR)**

Disappearance of all non-target lesions and normalization of tumor marker level. All lymph nodes must be non-pathological in size (< 10 mm short axis).

**Note:** If tumor markers are initially above the upper normal limit, they must normalize for a subject to be considered in complete clinical response.

**Non-CR/ Non-PD[Incomplete response/Stable Disease (SD)]**

Persistence of one or more non-target lesion(s) and/or maintenance of tumor marker level above the normal limits.

**Progressive Disease (PD)**

Appearance of one or more new lesions and/or *unequivocal progression* of existing non-target lesions. *Unequivocal progression* should not normally trump target lesion status. It must be representative of overall disease status change, not a single lesion increase. Although a clear progression of 'non-target' lesions only is exceptional, the opinion of the treating physician should prevail in such circumstances, and the progression status should be confirmed at a later time by the review panel (or Principal Investigator).

**11.2.4 Evaluation of Best Overall Response**

The best overall response is the best response recorded from the start of the treatment until disease progression/recurrence (taking as reference for progressive disease the smallest measurements recorded since the treatment started). The subject's best response assignment will depend on the achievement of both measurement and confirmation criteria.

## **12.0 RECORDS TO BE KEPT / REGULATORY CONSIDERATIONS**

Adverse event lists, guidelines, and instructions for AE reporting can be found in Section 8.0 (Adverse Events: List and Reporting Requirements).

### **12.1 Data Reporting**

The OnCore Database will be utilized, as required by the Case Comprehensive Cancer Center, to provide data collection for both accrual entry and trial data management. OnCore is a Clinical Trials Management System housed on secure servers maintained at Case Western Reserve University. OnCore properly used is compliant with Title 21 CFR Part 11. Access to data through OnCore is restricted by user accounts and assigned roles. Once logged into the OnCore system with a user ID and password, OnCore defines roles for each user which limits access to appropriate data. User information and password can be obtained by contacting the OnCore Administrator at [contact].

OnCore is designed with the capability for study setup, activation, tracking, reporting, data monitoring and review, and eligibility verification. This study will utilize electronic Case Report Form completion in the OnCore database. A calendar of events and required forms are available in OnCore.

### **12.2 Regulatory Considerations**

The study will be conducted in compliance with ICH guidelines and with all applicable federal (including 21 CFR parts 56 & 50), state or local laws.

#### **12.2.1 Written Informed consent**

Provision of written informed consent must be obtained prior to any study-related procedures. The Principal Investigator will ensure that the subject is given full and adequate oral and written information about the nature, purpose, possible risks and benefits of the study as well as the subject's financial responsibility. Subjects must also be notified that they are free to discontinue from the study at any time. The subject should be given the opportunity to ask questions and allowed time to consider the information provided.

The original, signed written Informed Consent Form must be kept with the Research Chart in conformance with the institution's standard operating procedures. A copy of the signed written Informed Consent Form must be given to the subject.

#### **12.2.2 Subject Data Protection**

In accordance with the Health Information Portability and Accountability Act (HIPAA), a subject must sign an authorization to release medical information to the sponsor and/or allow the sponsor, a regulatory authority, or Institutional Review Board access to subject's medical information that includes all hospital records relevant to the study, including subjects' medical history.

### **12.2.3 Retention of records**

The Principal Investigator of The Case Comprehensive Cancer Center supervises the retention of all documentation of adverse events, case report forms, source documents, records of study drug receipt and dispensation, and all IRB correspondence for as long as needed to comply with national and international regulations and the institution in which the study will be conducted, or for the period specified by the sponsor, whichever is longer. No records will be destroyed until the Principal Investigator confirms destruction is permitted.

### **12.2.4 Audits and inspections**

Authorized representatives of the sponsor, a regulatory authority, an Independent Ethics Committee (IEC) or an Institutional Review Board (IRB) may visit the Center to perform audits or inspections, including source data verification. The purpose of an audit or inspection is to systematically and independently examine all study-related activities and documents to determine whether these activities were conducted, and data were recorded, analysed, and accurately reported according to the protocol, Good Clinical Practice (GCP), guidelines of the International Conference on Harmonization (ICH), and any applicable regulatory requirements.

### **12.2.5 Data Safety and Monitoring Plan**

This protocol will adhere to the policies of the Case Comprehensive Cancer Center Data and Safety Monitoring Plan in accordance with NCI regulations.

## **13.0 STATISTICAL CONSIDERATIONS**

### **Overview**

This is a prospective, single arm Phase II study to determine the 3-month CNS –progression free survival **for patients with breast cancer with brain metastases treated with eribulin mesylate**, which is the primary objective of the study. To detect treatment response of brain metastases we will enroll 20 patients and use standard imaging modality, MRI, at baseline and 12 weeks.

### **Sample size and study duration**

Clinically, in this population of breast cancer with brain metastases, we expect that a therapy would induce a 35% 3-month PFS rate. A 15% rate would not be considered meaningful, and thus anything statistically significant > 15% would be considered a positive study. The 3-month CNS PFS of 35% as an indicator of efficacy was based on studies of chemotherapy in brain metastases, which demonstrated 3-month CNS PFS rates in the range of 22%–50% (34-36). If 8 or more patients (out of 20) remain progression free at three months this will be taken as evidence that eribulin may have a positive impact on PFS, as the estimate of the proportion of patients with PFS would be 40%, and the 95% CI would be 18.5-61.5%, which does not include 15%. Thus, we have determined that a total of 20 evaluable patients will be required for the study.

In terms of availability of patients to enroll in this study, the proposed institution for this trial is the Case Comprehensive Cancer Center, a collaboration that includes clinical research activities at both University Hospitals Siedman Cancer Center and the Cleveland Clinic Foundation.

Approximately 9000 new cancer patients are seen at Case Comprehensive Cancer Center annually of which 30-40 patients have brain metastases from metastatic breast cancer in Seidman network

alone. The anticipated accrual rate is 20 patients per year. We have the predefined response on eribulin mesylate which will be assessed by CNS RECIST 1.1 criteria using MRI scan.

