### **3.4. Duration of Therapy**

In the absence of treatment delays due to adverse events, treatment may continue on study until one of the following criteria applies:

- Systemic or CNS disease progression,
- Intercurrent illness that prevents further administration of treatment,
- The investigator considers it, for safety reasons, to be in the best interest of the patient.
- Unacceptable treatment related toxicity, NCI CTC AE version 4.0. Grade 3 or 4 that fails to recover to baseline or < Grade 2 in the absence of treatment within 4 weeks
- General or specific changes in the patient's condition render the patient unacceptable for further treatment in the judgment of the investigator,
- Patient decision to withdraw from treatment (partial consent) or from the study (full consent),
- Pregnancy during the course of the study
- Death

The date and reason for discontinuation must be documented. Every effort should be made to complete the appropriate assessments.

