### **3.6 Replacement of Subjects**

Subjects who do not obtain the two MRI scans (baseline and 12 weeks) will be considered not evaluable for response and will be replaced.

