### **Evaluability**

To be evaluable for inclusion in the primary objective and secondary objectives, patients must have baseline and week 12 MRI.

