### **13.1 Methods to address the study objectives**

#### **Primary Objective:** CNS PFS at 3 months

We will assess the proportion of subjects without CNS progression at 3 months. We hypothesize that this will be at least 35%. We will generate a Kaplan-Meier curve of CNS PFS and estimate the PFS and 95% CI of the PFS.

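### Patients who die or progress in the CNS before the week-12 MRI can be replaced instead of counted as failures, which biases the 3-month CNS PFS rate upward

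*Combined protocol and SAP*

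**What the plan says.** **Who is counted.** The Evaluability paragraph of Section 13.0 covers the primary and secondary objectives alike: "patients must have baseline and week 12 MRI". Section 3.6 says that subjects without the two scans "will be considered not evaluable for response and will be replaced". Neither mentions death or progression.

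**Who gets the scan.** Section 3.4 ends treatment on "Systemic or CNS disease progression", among other reasons, and asks for every effort to complete assessments. Footnote d of the calendar (Section 10.2) ties the 12-weekly brain MRI to being on eribulin. Section 11.1 plans an MRI after 12 weeks. Section 11.1.4 plans one at 12 weeks and then 12-weekly until progression.

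**A different evaluability rule.** Section 11.1.1, on objective response, treats as evaluable those patients with measurable disease who were treated per protocol and re-evaluated. It adds those who progress before the end of cycle 1.

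**The decision rule.** Under Sample size and study duration, 15% is not meaningful and 35% is expected; "thus anything statistically significant > 15% would be considered a positive study". Then: "If 8 or more patients (out of 20) remain progression free at three months this will be taken as evidence" of a positive effect, because at 8/20 "the 95% CI would be 18.5-61.5%, which does not include 15" (per cent). Section 13.1 says of the 3-month proportion "We hypothesize that this will be at least 35" (per cent) and adds: "We will generate a Kaplan-Meier curve of CNS PFS and estimate the PFS and 95% CI of the PFS". No alpha, power, test or form of interval is named.

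**The concern.** For a progression-free survival endpoint, an early CNS progression or death is the outcome being measured. It is not missing data. I take PFS in its usual sense, with death as an event; Section 13.1 does not spell this out. A rule that admits only patients with a week-12 scan selects those who got that far, and replacement fills the gaps with others who also got that far. The bias runs one way, towards a higher rate.

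The population makes this plausible: Section 1.4 cites median survival of about 4 months after brain metastases from triple-negative disease, and 4-7.5 months by subtype. The Kaplan-Meier curve does not help if it is drawn on the same evaluable set. At stake is whether 8/20 means 40% of patients treated or 40% of those who stayed to be scanned.

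A second gap is that the operating characteristics of the 8/20 rule are nowhere stated, so a reader cannot judge what a positive or a negative result is worth.

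**Working it through.** **Step 1. Can an early failure lack the scan?** Take a patient with CNS progression at week 7, shown on an unscheduled MRI or by neurological worsening (Section 11.1.4.1 counts new or worsening tumour-related neurological symptoms as progression). Section 3.4 stops treatment. Calendar footnote d no longer applies, and the Section 11.1.4 schedule runs only until progression. Unless someone obtains a week-12 MRI anyway, the patient has one scan, is not evaluable under Section 13.0, and is replaced under Section 3.6. A patient who dies at week 7 is replaced for certain.

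**Step 2. Reproduce the plan's interval.** Inputs: 8/20 and a 95% level. Wald: 0.40 ± 1.96 × √(0.40 × 0.60 / 20) = 0.40 ± 1.96 × 0.1095 = 18.5-61.5%. This matches. At 7/20: 0.35 ± 1.96 × 0.1067 = 14.1-55.9%, which includes 15%. So under the plan's own interval, 8 is the smallest count that excludes 15%.

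**Step 3. The rule with all 20 counted and none replaced.** Exact binomial, P(X ≥ 8), n = 20:

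| True rate | P(X ≥ 8) |
|---|---|
| 15% | 0.0059 (alpha 0.6%) |
| 35% | 0.399 (power 39.9%) |
| 40% | 0.584 |
| 46.9% | 0.80 |
| 50% | 0.868 |

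**Step 4. Put replaced failures back.** Suppose 8/20 is observed after k early failures were replaced (k is assumed; the documents give no figure). The rate with all counted is 8/(20 + k):

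| k | Rate | Wald 95% CI | Exact (Clopper-Pearson) 95% CI |
|---|---|---|---|
| 0 | 40.0% | 18.5-61.5% | 19.1-63.9% |
| 3 | 34.8% | 15.3-54.2% | 16.4-57.3% |
| 4 | 33.3% | 14.5-52.2% | 15.6-55.3% |
| 5 | 32.0% | 13.7-50.3% | 14.9-53.5% |

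The interval first includes 15% at k = 4 by the plan's Wald method, and at k = 5 by the exact method.

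**Step 5. False-positive rate under replacement.** Let f be the share of enrolled patients who are early failures and are replaced (assumed). A true all-patient rate of 15% becomes 0.15 / (1 − f) among those counted, and the false-positive rate is P(X ≥ 8) at that value:

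| f | Rate among counted | False-positive rate |
|---|---|---|
| 0 | 15.0% | 0.6% |
| 5% | 15.8% | 0.8% |
| 10% | 16.7% | 1.1% |
| 20% | 18.8% | 2.2% |
| 30% | 21.4% | 4.7% |

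**The case against.** **Many early stoppers will be scanned.** Sections 11.1 and 11.1.4 plan the 12-week MRI without tying it to being on drug, and Section 3.4 asks for assessments to be completed. Section 4.1.6 also excludes patients whose life expectancy might be under 3 months because of uncontrolled systemic disease or tumour complications. This stands in part. A reader might infer that every early failure is replaced; the documents do not support that, since one who still has the week-12 scan is counted. But no provision brings back a patient who died, and nothing requires a scan after CNS progression is already established.

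**Section 11.1.1 may protect early progressors.** It does call re-evaluated patients evaluable, and cycle-1 progressors too. But it defines evaluability for objective response, whereas the Section 13.0 paragraph names the primary objective. The two need reconciling.

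**The numerical effect is modest.** Fair. At 20% replacement the false-positive rate is still 2.2%, because the cut-off is strict to begin with. At 8/24 the exact interval still excludes 15%; only the Wald interval does not. The bias in the estimate itself remains: 33.3% reported as 40%.

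**Does the plan contain two conflicting success criteria?** A reader might infer so, because at 7/20 the Clopper-Pearson interval is 15.4-59.2% and excludes 15%, although the count rule fails. The documents do not support this as a contradiction. Under the Wald interval they evidently used, 7/20 includes 15% and the two statements agree. The difference appears only when another interval is brought in. What is missing is a sentence saying which statement governs.

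**Conclusion.** The concern holds as a fault in who is counted. Sections 3.6 and 13.0, followed as written, allow deaths and CNS progressions before week 12 to leave the primary analysis and be replaced. The direction, upward, is certain for any such patient; the size is not known. On assumed shares of 5% to 30% replaced, the false-positive rate of the 8/20 rule goes from 0.6% to 0.8-4.7%. An 8/20 result would fall to 33.3% after 4 replaced failures and 32.0% after 5. These figures assume that every replaced patient was a failure and that 15% is meant as a rate among all patients, which the plan does not say.

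Two stronger readings fail. The plan's interval of 18.5-61.5% is computed correctly, and the 8/20 rule is conservative when all 20 patients are counted. The secondary point is one of disclosure: a drug that performs exactly at the hypothesised 35% would be declared positive only 39.9% of the time, and the plan does not say so.

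**What to change.** By short amendment:

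1. In Section 3.6 and the Evaluability paragraph of Section 13.0, state that patients who die or have documented CNS progression before the week-12 MRI count as failures in the primary analysis and are not replaced. Align Section 11.1.1 with this.
2. Report the number of any other replaced patients, with reasons. Add a sensitivity analysis that counts every treated patient without a week-12 MRI as a failure.
3. Keep 8/20 as the single decision rule, and say that the count governs and that all confidence intervals, including the Kaplan-Meier one, are descriptive. Do not add an exact test with a Clopper-Pearson interval as a co-primary method: at 7/20 it would contradict the count rule.
4. State the exact operating characteristics: alpha 0.6% at 15%, power 39.9% at 35%, and 80% power only at a true rate of about 46.9%. Describe them as holding among the 20 counted patients. Patients lost for other reasons (systemic progression, toxicity, withdrawal) may still be replaced, so they are not strictly all-patient rates.

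Cost: no extra patients, and fewer replacements. The observed rate may be lower and 8/20 harder to reach, and the stated power will look unfavourable.
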